7.1 Procedures by Visit

Written informed consent must be obtained prior to any study required procedures that would not have been performed as part of normal patient care at the site.

7.1.1 Pre-Study

Prior to randomization, patients will complete the informed consent process and have all required protocol assessments completed in order to assess eligibility requirements. All procedures and an assessment of eligibility should be documented in the patient record.

Within ≤ 4 weeks of randomization to protocol therapy:

- Medical history
- Assessment of baseline signs and symptoms
- Physical examination
- Concomitant medication assessment (see Appendix C for list of excluded or medications requiring monitoring on study)
- Vital signs, including blood pressure, heart rate and temperature, height and weight
- Assessment of ECOG performance status
- Imaging scans for complete disease assessment. Care should be taken to continue to use the same evaluation method during the study as used for initial evaluation. See Section 6 for additional details.
- PT with INR
- Urinalysis
- CBC with differential and platelets
- Serum Creatinine, Electrolytes (K, Na, Cl, CO₂), Ca, BUN, Albumin, Total Protein, Phosphorus, AST (SGOT), ALT (SGPT), Alkaline Phosphatase, Total Bilirubin, Magnesium and Uric Acid
- Fasting Glucose
- Fasting Serum Lipid Profile (triglycerides, total cholesterol, HDL and LDL)

A detailed assessment of hepatitis B/C medical history and risk factors must be done for all patients. Patients with positive hepatitis B and/or hepatitis C test results must begin a course of antivirals within 1-2 weeks prior to the first dose of everolimus (as outlined in Section 5.3.2.2 and 5.3.2.3).

Testing for hepatitis B viral load and serologic markers: HBV-DNA, HBsAg, HBsAb, HBcAb and HCV RNA-PCR are required at screening for all patients in the following risk categories:

- All patients who have lived in Asia, Africa, Central and South America, Eastern Europe, Spain, Portugal, and Greece.
[<http://wwwnc.cdc.gov/travel/yellowbook/2012/chapter-3-infectious-diseases-related-to-travel/hepatitis-b.htm>]

- Patients with any of the following risk factors:
 - known or suspected past hepatitis B infection
 - blood transfusion(s) prior to 1990
 - current or prior IV drug users
 - current or prior dialysis
 - household contact with hepatitis B infected patient(s)
 - current or prior high-risk sexual activity
 - body piercing or tattoos
 - mother known to have hepatitis B
 - history suggestive of hepatitis B infection, e.g., dark urine, jaundice, right upper quadrant pain.
- Additional patients at the discretion of the investigator

Testing for hepatitis C should be performed using quantitative RNA-PCR at screening for all patients in the following risk categories:

- known or suspected past hepatitis C infection (including patients with past interferon 'curative' treatment)
- blood transfusions prior to 1990
- current or prior IV drug users
- current or prior dialysis
- household contact of hepatitis C infected patient(s)
- current or prior high-risk sexual activity
- body piercing or tattoos
- At the discretion of the investigator, additional patients may also be tested for hepatitis C.

Final determination of eligibility and randomization to therapy should be done only after all assessments are completed.

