5.3.2.2 Monitoring and Prophylactic Treatment for Hepatitis B Reactivation

Table 5-3 provides details of monitoring and prophylactic therapy according to the baseline results of viral load and serologic markers testing.

Table 5-3

Action to be Taken for Positive Baseline Hepatitis B Results

Test	Result	Result	Result	Result	Result
HBV-DNA	+	+ or -	-	-	-
HBsAg	+ or -	+	-	-	-
HBsAb	+ or -	+ or -	+ and no prior HBV vaccination	+ or -	or + with prior HBV vaccination
HBcAb	+ or -	+ or -	+ or -	+	-
Recommendation	Prophylaxis treatment should be started 1-2 weeks prior to first dose of study drug Monitor HBV-DNA approximately every 4-8 weeks		No prophylaxis Monitor HBV-DNA approximately every 3-4 weeks		No specific action

Antiviral prophylaxis therapy should continue for at least 4 weeks after last dose of study drug.

For hepatitis B reactivation, definition and management guidelines see Table 5-4 Guidelines for Management of Hepatitis B.

Table 5-4**Guidelines for Management of Hepatitis B**

HBV Reactivation (with or without clinical signs and symptoms)*	

For patients with baseline results:
 
Positive HBV-DNA
 
OR
 
Positive HBsAg
 <hr/> 
Reactivation is defined as:
 
Increase of 1 log in HBV-DNA relative to baseline HBV-DNA value OR new appearance of measurable HBV-DNA
	
Treat: Start a second antiviral
 
AND
 
Interrupt study drug administration until resolution: \leq baseline HBV-DNA levels
 
If resolution occurs within \leq 21 days, study drug should be restarted at one dose lower, if available. If the patient is already receiving the lowest dose of study drug according to the protocol, the patient should restart at the same dose after resolution. Both antiviral therapies should continue at least 4 weeks after last dose of study drug.
 
If resolution occurs >21 days, patients should discontinue study drug but continue both antiviral therapies at least 4 weeks after last dose of study drug.

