5.3.2.3 Monitoring for Hepatitis C Flare

The following two categories of patients should be monitored every 4-8 weeks for HCV reactivation:

- Patients with detectable HCV RNA-PCR test at baseline.

- Patients known to have a history of HCV infection, despite a negative viral load test at baseline (including those that were treated and are considered 'cured').

For definition of hepatitis C flare and the management guidelines, see Table 5-5 Guidelines for Management of Hepatitis C.

Table 5-5

Guidelines for Management of Hepatitis C

HCV Flare*	

For patients with baseline results:
 
Detectable HCV-RNA:
 
HCV Flare is defined as:
 
$>2 \log_{10}$ IU/mL increase in HCV-RNA
 
AND
 
ALT elevation $>5x$ ULN or 3x baseline level, whichever is higher
	Discontinue study drug.

For patients with baseline results:
 
Knowledge of past hepatitis C infection with no detectable HCV-RNA:
 
HCV Flare is defined as:
 
New appearance of detectable HCV-RNA
 
AND
 
ALT elevation $>5x$ ULN or 3x baseline level, whichever is higher
	Discontinue study drug.

* All flares of hepatitis C are to be recorded as grade 3 (CTEP CTCAE Version 4.0. Metabolic Laboratory/Other: Viral Flare), unless considered life threatening by the investigator; in which case they should be recorded as grade 4 (CTEP CTCAE Version 4.0 Metabolic Laboratory/Other: Viral Flare).

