5.3.4 Prohibited Therapies and Restrictions

The following restrictions apply during the entire duration of the study:

- No other investigational therapy should be given to patients.
- No anticancer agents other than the study medication should be given to patients, with the following exceptions:
 - Bisphosphonates, Zometa, or Xgeva for bone metastases
 - a GnRH analog is permitted if the patient had progressive disease on a GnRH analog plus a SERM or an AI; the GnRH analog may continue but the SERM or AI must be discontinued.
- If any other anticancer agents are required for a patient then the patient must first be withdrawn from the study.
- Concurrent radiation therapy is prohibited, however palliative radiotherapy may be considered on a case by case basis after discussion with the Study Chair.
- Patients must not be receiving chronic, systemic treatment with corticosteroids or another immunosuppressive agent greater than or equal to 5 mg prednisone or its equivalent daily. Topical or inhaled corticosteroids are allowed.
- The use of live vaccines and close contact with those who have received live vaccines should be avoided during treatment with everolimus. Examples of live vaccines include intranasal influenza, measles, mumps, rubella, oral polio, BCG, yellow fever, varicella and TY21a typhoid vaccines.
- It is highly recommended that patients with positive HBV-DNA or HBsAg are treated prophylactically with an antiviral for 1-2 weeks prior to receiving study drug (see Table 5-3).
- The antiviral treatment should continue throughout the entire study period and for at least 4 weeks after the last dose of study drug.
- Patients on antiviral prophylaxis treatment or positive HBV antibodies should be tested for HBV-DNA according to study visit schedule.
- Oral contraceptives in preclinical and clinical data have shown everolimus to have CYP3A4 inhibitory activity rather than induction activity, induction of metabolism of contraceptive hormones by everolimus is unlikely. Consequently, administration of everolimus should not reduce the efficacy of oral contraceptives.
- Grapefruit and other citrus juices affect P450 and PgP activity. Concomitant use should be avoided.

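### Protocol 7.1.1 makes pre-treatment antivirals mandatory after positive hepatitis B or C results and cites 5.3.2.2 and 5.3.2.3, but those sections do not contain that rule

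*Protocol*

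**What the plan says.** Protocol 7.1.1 (Pre-Study) states that patients whose hepatitis B or C tests come back positive "must begin a course of antivirals within 1-2 weeks prior to the first dose of everolimus". The sentence closes with a cross-reference in brackets: "as outlined in Section 5.3.2.2 and 5.3.2.3". The next paragraph of 7.1.1 defines the tests: "Testing for hepatitis B viral load and serologic markers: HBV-DNA, HBsAg, HBsAb, HBcAb and HCV RNA-PCR are required at screening" for patients in listed risk categories.

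The other passages read as follows.

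- **Table 5-3 (5.3.2.2), HBV-DNA or HBsAg positive:** "Prophylaxis treatment should be started 1-2 weeks prior to first dose of study drug".
- **Table 5-3, HBV-DNA and HBsAg negative, with HBcAb positive or HBsAb positive without vaccination:** "No prophylaxis Monitor HBV-DNA approximately every 3-4 weeks".
- **Table 5-3, HBsAb positive after vaccination, other markers negative:** no specific action.
- **Table 5-4:** at reactivation, the antibody-only group starts its first antiviral, and the HBV-DNA or HBsAg positive group starts a second one.
- **5.3.2.3:** "The following two categories of patients should be monitored every 4-8 weeks for HCV reactivation". Table 5-5 adds discontinuation of study drug if a flare occurs.
- **5.3.4:** "It is highly recommended that patients with positive HBV-DNA or HBsAg are treated prophylactically with an antiviral". Footnote f of the Section 7 study table gives the same recommendation for the same patients.

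**The concern.** Section 7.1.1 is the list of screening procedures that a site works from. Its sentence is mandatory, covers both viruses, and does not separate one kind of positive result from another. A site that follows it literally would start antivirals in patients whom Section 5 only monitors. A site that goes straight to Section 5 would not.

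This bears on patient safety. Section 5.3.2 reports hepatitis B reactivation under everolimus and says that some infections were severe or fatal. It also says that antivirals reduce the risk of reactivation. Under Tables 5-4 and 5-5, reactivation or flare leads to interruption or discontinuation of study drug. Section 11.1 requires conduct as described in the protocol, and here the protocol can be read in two ways.

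**Working it through.** No arithmetic applies. The check sets 7.1.1, read literally, against Section 5 and the study table for each baseline result.

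| Baseline result | 7.1.1, read literally | Elsewhere in the protocol |
|---|---|---|
| HBV-DNA+ or HBsAg+ | Antivirals, mandatory | Table 5-3: prophylaxis (*should*). 5.3.4 and footnote f: prophylaxis (recommended) |
| HBV-DNA− and HBsAg−, with HBcAb+ or HBsAb+ without vaccination | Antivirals, mandatory | Table 5-3: no prophylaxis, monitor. Table 5-4: first antiviral at reactivation |
| HBsAb+ after vaccination, other markers negative | Antivirals, mandatory | Table 5-3: no specific action |
| HCV RNA detectable | Antivirals, mandatory | 5.3.2.3: monitor. Table 5-5: discontinue study drug on flare. No antiviral step |

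1. **Hepatitis C (row 4).** 7.1.1 names hepatitis C and cites 5.3.2.3. That section and its table contain no antiviral instruction for anyone, so the cross-reference leads to nothing. The only hepatitis C test in 7.1.1 is RNA-PCR. The sentence therefore reaches patients with detectable RNA, the first of the two groups in 5.3.2.3, and not those with past infection and a negative test.

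2. **Antibody-only hepatitis B (rows 2 and 3).** 7.1.1 lists HBsAb and HBcAb among the hepatitis B tests, so an antibody-only result is a positive hepatitis B result on its face. Table 5-3 withholds prophylaxis in row 2 and calls for nothing in row 3. Table 5-4 assumes that the row 2 group is untreated, because its step at reactivation is a first antiviral. That step cannot be applied as written to a patient already treated under 7.1.1.

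3. **Strength and timing (row 1).** All passages point to the same action. The strength runs from *must* (7.1.1) through *should* (Table 5-3) to a recommendation (5.3.4, footnote f). Table 5-4 prescribes a second antiviral for this group, which presupposes a first; a patient left untreated under a mere recommendation would not fit that step. On timing, 7.1.1 has the course begin within the 1-2 weeks before the first dose, while 5.3.4 and footnote f describe treatment lasting 1-2 weeks before study drug.

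**The case against.** The strongest reply is that 7.1.1 is a visit checklist and that its cross-reference hands the question of who is treated to Section 5. A site that follows it reaches Table 5-3, which gives a rule for each hepatitis B result. The rest of the protocol fits this reading. Table 5-3, 5.3.4 and footnote f all confine prophylaxis to HBV-DNA or HBsAg positive patients. Footnote g, 7.1.2.1 and 7.1.2.3 name patients on prophylaxis and patients with positive antibodies as alternatives. On this view the hepatitis B scheme is coherent and 7.1.1 is one loosely worded sentence. That reply stands as a reasonable reading of the hepatitis B part, but it leaves the hepatitis C part and the differences in strength and timing where they were.

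A reader might also say that such patients are excluded. Exclusion criterion 13 does bar active or uncontrolled severe infections and cirrhosis or severe hepatic impairment, which may shrink the group. But 5.3.2.3 and 7.1.2.1 plan on-study monitoring of patients with detectable HCV RNA, and Tables 5-3 and 5-4 plan for hepatitis B positive patients, so the protocol expects some on study.

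Three stronger inferences are tempting and are not supported.

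- **That 7.1.1 covers any positive result in terms.** It does not use that word. It is unqualified, and a cross-reference follows.
- **That the same patient always gets opposite instructions.** 5.3.2.3 is silent on antivirals rather than opposed to them, and for HBV-DNA or HBsAg positive patients the wording differs in strength, not direction.
- **That the treatment comparison is biased.** Assignment is randomized and blinded, and both arms follow the same hepatitis instructions. Nor do the documents say that either course would be recorded as a deviation.

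**Conclusion.** The sentence in 7.1.1 is wrong as written: it is an internal inconsistency, not a design choice. The hepatitis C part is firm, because the cited section contains nothing that supports the instruction. The antibody-only hepatitis B part is a conflict on the literal reading and an ambiguity if the cross-reference is taken as limiting. The differences in strength and timing are secondary.

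The number of patients affected is not given. It is probably small, since 7.1.1 requires testing only in listed risk categories, with others at the investigator's discretion. There is no effect on the sample size or the primary analysis. The point merits correction because it bears on patient safety and the protocol can be followed in more than one way.

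**What to change.** Reconcile the 7.1.1 sentence with Tables 5-3 and 5-4, 5.3.2.3, 5.3.4 and study-table footnote f, so that each baseline hepatitis result leads to one instruction with one strength and one timing. For hepatitis C, 7.1.1 and 5.3.2.3 must say the same thing. Which rule applies to each result is for the sponsor's clinical team, and none is proposed here. If footnote f changes, the copy in SAP Appendix 2 should follow.

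The cost is wording at the next protocol amendment. No analysis, sample size or data collection changes because of the reconciliation itself.

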7.1.2 Induction Phase (fulvestrant + everolimus/placebo)

Day 1 of each cycle is defined as the day in which fulvestrant is given, including the first fulvestrant dose, third fulvestrant dose, and every dose thereafter (the second fulvestrant doses is given on day 15 of the first cycle only). **Note:** If patient previously received one cycle of fulvestrant (day 1 and day 15) prior to study entry as permitted in Inclusion Criteria #8, patient should receive fulvestrant 500 mg on day 1 only.

Patients will be assessed continually for toxicity and study continuation. Protocol therapy doses should be calculated and modified as per Section 5. Assessment of disease for response should be performed as per Section 6.

One cycle in the Induction Phase is equal to 28 days. Patients are treated for a maximum of 12 cycles in the Induction Phase.

7.1.2.1 *Within 7 Days of Cycle 1 Day 1*

Note: The following assessments do not have to be repeated if the pre-study assessments were performed within ≤ 7 days of Cycle 1 Day 1.

- Physical examination
- Concomitant medication assessment (see Appendix C for list of excluded or medications requiring monitoring on study)
- Vital signs, including blood pressure, heart rate, temperature and weight
- Assessment of ECOG performance status
- Adverse event assessment and dose modifications as necessary (AEs should be monitored continuously). AE assessment should begin after the first dose of study medication has been administered.
- CBC with differential and platelets
- Serum Creatinine, Electrolytes (K, Na, Cl, CO₂), Ca, BUN, Albumin, Total Protein, Phosphorus, AST (SGOT), ALT (SGPT), Alkaline Phosphatase, Total Bilirubin, Magnesium and Uric Acid
- Fasting Glucose
- Fasting Serum Lipid Profile (triglycerides, total cholesterol, HDL and LDL)
- Patients on antiviral prophylaxis treatment or positive HBV antibodies should be tested for HBV-DNA on Cycle 1 Day 1 and Day 1 of all subsequent cycles (every 28 days) to monitor for re-activation. If re-activation is confirmed, everolimus must be interrupted or discontinued according to the guidance in Table 5-4. Patients with positive HCV RNA-PCR results at screening and/or a history of past infection (even if treated and considered 'cured') should have HCV RNA-PCR testing performed on Cycle 1 Day 1 and Day 1 of all subsequent cycles (every 28 days) to monitor for flare. Everolimus must be discontinued if HCV reactivation is confirmed according to the guidance in Table 5-5.

7.1.2.2 Cycle 1 Day 15

- Physical examination
- Concomitant medication assessment (see Appendix C for list of excluded or medications requiring monitoring on study)
- Vital signs, including blood pressure, heart rate, temperature, and weight
- Assessment of ECOG performance status
- Adverse event assessment and dose modifications as necessary (AEs should be monitored continuously). (see Section 5.3 for dose modification guidelines)
- CBC with differential and platelets. In the event of grade 3 or 4 hematologic toxicity, CBC with differential and platelet count will be obtained every 1-3 days until there is evidence of hematologic recovery.
- Serum Creatinine, Electrolytes (K, Na, Cl, CO₂), Ca, BUN, Albumin, Total Protein, Phosphorus, AST (SGOT), ALT (SGPT), Alkaline Phosphatase, Total Bilirubin, Magnesium and Uric Acid
- Study Drug Compliance (Pill Diary) for everolimus/placebo

7.1.2.3 Cycle 2 (and each subsequent cycle) Day 1

- Physical examination
- Concomitant medication assessment (see Appendix C for list of excluded or medications requiring monitoring on study)
- Vital signs, including blood pressure, heart rate, temperature and weight
- Assessment of ECOG performance status
- Adverse event assessment and dose modifications as necessary (AEs should be monitored continuously, see Section 5.3 for dose modification guidelines).
- CBC with differential and platelets. In the event of grade 3 or 4 hematologic toxicity, CBC with differential and platelet count will be obtained every 1-3 days until there is evidence of hematologic recovery.
- Serum Creatinine, Electrolytes (K, Na, Cl, CO₂), Ca, BUN, Albumin, Total Protein, Phosphorus, AST (SGOT), ALT (SGPT), Alkaline Phosphatase, Total Bilirubin, Magnesium and Uric Acid
- Fasting Glucose (Cycle 2 Day 1, then every 12 weeks during treatment, and more frequently as clinically indicated)
- Fasting Serum Lipid Profile (triglycerides, total cholesterol, HDL and LDL) (Cycle 2 Day 1, then every 12 weeks during treatment, and more frequently as clinically indicated)
- Patients on antiviral prophylaxis treatment or positive HBV antibodies should be tested for HBV-DNA on Cycle 1 Day 1 and Day 1 of all subsequent cycles (every 28 days) to monitor for re-activation. If re-activation is confirmed, everolimus must be interrupted or discontinued according to the guidance in Table 5-4. Patients with positive HCV RNA-PCR results at screening and/or a history of past infection (even if treated and considered 'cured') should have HCV RNA-PCR testing performed on Cycle 1 Day 1 and Day 1 of all subsequent cycles (every 28 days) to monitor for flare. Everolimus must be discontinued if HCV reactivation is confirmed according to the guidance in Table 5-5.
- Study Drug Compliance (Pill Diary) for everolimus/placebo

7.1.2.4 Every 12 Weeks

- Tumor evaluation every 12 weeks, +/- 1 week (every 3 months) during the Induction Phase. Scans should be repeated at the assigned intervals regardless of cycle or treatment delays.
- Fasting Glucose and Fasting Serum Lipid Profile (triglycerides, total cholesterol, HDL and LDL) to be done every 12 weeks during Induction Phase (and more frequently as clinically indicated)

7.1.3 End of Induction Phase <OR> End of Treatment

All patients will have the following assessments completed whether they are moving into the Continuation Phase or no longer will be receiving treatment and are moving into Follow-Up Off-Therapy due to reasons noted in Sections 5.5 or 5.6. The assessments should be completed within 30 days of last dose of fulvestrant and before moving from the Induction Phase into the Continuation Phase or before moving directly into the Follow-Up Phase. (**Note:** Day 1 of the Continuation Phase should start on D29 of cycle 12 if the assessments below are completed in order to maintain the 28 day fulvestrant dosing schedule).

- Physical examination
- Concomitant medication assessment (see Appendix C for list of excluded or medications requiring monitoring on study)
- Vital signs, including blood pressure, heart rate, temperature and weight
- Assessment of ECOG performance status
- Adverse event assessment. All patients will be followed for toxicity assessment for 30 days after the last dose of study therapy (fulvestrant and/or everolimus/placebo) or until resolution to \leq grade 1 attributed to study therapy (or if $>$ grade 1, event must be permanent and stable). Serious adverse events >30 days after last dose of fulvestrant and/or everolimus/placebo are not reported unless the event may be related to everolimus/placebo.
- Tumor evaluation if due per every 12 weeks +/- 1 week (every 3 months) evaluation schedule.
- CBC with differential and platelets
- Serum Creatinine, Electrolytes (K, Na, Cl, CO₂), Ca, BUN, Albumin, Total Protein, Phosphorus, AST (SGOT), ALT (SGPT), Alkaline Phosphatase, Total Bilirubin, Magnesium and Uric Acid
- Fasting Glucose
- Fasting Serum Lipid Profile (triglycerides, total cholesterol, HDL and LDL)
- Study Drug Compliance (Pill Diary) for everolimus/placebo

Patients in the Continuation Phase should continue to receive fulvestrant alone (if originally randomized to placebo) or in combination with everolimus (if originally randomized to everolimus) at the same dose and schedule until disease progression or unacceptable toxicity.

Patients that are moving from the Induction Phase into Follow-Up Off Therapy should not receive further investigational therapies for at least 30 days after the last dose of study drug, if possible, in order to eliminate overlapping toxicity.

